STUDY PROTOCOL: THRIVE AND LARYNGOLOGIC SURGERY

1

**The Safety and Efficacy of the Transnasal Humidified Rapid-Insufflation Ventilatory Exchange (THRIVE)
for Short Laryngologic Surgical Procedures**

Study Protocol

NCT03091179

February 15, 2017

STUDY PROTOCOL: THRIVE AND LARYNGOLOGIC SURGERY

STUDY OBJECTIVES

1. DETERMINING THE SAFETY AND EFFICACY OF THRIVE FOR SHORT LARYNGOLOGIC SURGERY.

THRIVE should improve operating conditions, decrease surgical time, and potentially lead to better patient outcomes. The safety of THRIVE for short laryngologic surgery has not been formally investigated, and will be explored in this study. With the patient anesthetized, apneic, and adequately oxygenated with THRIVE, the build up of carbon dioxide in patient's blood (PaCO_2) and ensuing acute hypercapnic acidosis will be the main factors limiting the duration of THRIVE administration. At present, the rate of PaCO_2 rise with THRIVE has not been directly investigated, but is suggested to be between 1.1 and 1.8 mm Hg per minute. It is expected that the short duration of laryngologic procedures explored in this study (not exceeding 30 min) will not lead to substantial rise of PaCO_2 . The PaCO_2 rise to 75 mm Hg is considered a safe level for moderate hypercapnia in patients without significant comorbidities (see Exclusion Criteria).

2. DETERMINING POSSIBLE BENEFICIAL EFFECT OF THRIVE ON IMMEDIATE POSTOPERATIVE RECOVERY in PACU, QUALITY OF POSTOPERATIVE RECOVERY (QoR15), OPIOD CONSUMTION, AND VOICE HANDICAP INDEX (VHI-10).

EXCLUSION CRITERIA

1. Patients with significantly decreased myocardial function (ejection fraction < 50%)
2. Patients with abnormal cardiac rhythm and conduction abnormalities, except for patients with isolated, asymptomatic premature atrial and ventricular contractions.
3. Patients with significant peripheral vascular disease, such as those with the symptoms of intermittent claudication.
4. Patients with known significant cerebrovascular disease, such as history of cerebrovascular accidents (CVAs) and transient ischemic attacks (TIAs).
5. Patients with significant renal insufficiency, as manifested by estimated glomerular filtration rate (eGFR) < 60 ml/min/1.73 m².
6. Patients with electrolyte (K+, Ca++) abnormalities, as determined by the lab values outside of a normal range.

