xiv. Functional home recovery profile after surgery during first postop week

- Pain scores
- PO opioid requirements
- PO non-opioid (Tylenol) requirements
- QoR15
- Return to daily activities
- Return to work

xv. VHI-10 (Voice Handicap Index)

- Preop vs 1 month after surgery

STUDY PROTOCOL: THRIVE AND LARYNGOLOGIC SURGERY

OPERATING ROOM PREPARATION

1. All drugs, airway supplies, eye tape, per routine.
2. 5.0 MLT ETT.
3. Precut large Tegaderm for securing ETT to the chin in left corner of mouth.
4. Video laryngoscopy system: either a Glidescope or Storz CMAC system.
5. Monsoon JV with connection tubing for suspension laryngoscope, and full humidification set up.
6. Four channel Alaris pump with:
 - a. NS carrier at 50 ml/hr
 - b. Propofol drip
 - c. Remifentanil drip
 - d. Check to assure tight connections throughout
7. 20 ml NS syringe in-line for chasing the induction and IVP drugs intraop. **Please minimize IVF beyond 10 ml/kg total (5 ml/kg prior to induction, and 5 ml/kg as required intraoperatively), due to high incidence of urinary retention in male patients.**
8. Working PNS with pads (make sure the battery is fresh).
9. Sedline monitor.

STUDY PROTOCOL: THRIVE AND LARYNGOLOGIC SURGERY

	THRIVE GROUP	CONTROL GROUP
PREOP and PREMEDICATION	
 • Obtain patient's consent. Make 2 copies: one for the chart, and another for the patient. • Randomize the patient to either THRIVE or CONTROL group (5.0 MLT or supraglottic jet). Note: patient is blinded to the modality used. • Obtain preop VAS pain score, QoR15 and VHI. • Patient's folder contains: a copy of consent, postop diaries, QoR15, VHI, all stamped with patient's stickers, and 3 return, pre-stamped envelopes. Enter DOS and subject # in diaries, QoR15, VHI. • Study folder contains: consent, preop QoR15, VHI, intraop and PACU data collection sheets, all stamped with patient's stickers. Place patient's sticker on study folder. • Peripheral IV, 20 g R upper extremity (preferred), tape securely straight out. • Midazolam 0.007 mg/kg incremental doses to achieve sufficient anxiolysis, not to exceed 0.025 mg/kg total dose, unless severe anxiety. For elderly patients (70-80 y.o), limit total dose of Midazolam to 0.5 mg. 	

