	
• Maintain THRIVE at 70 l/min with jaw thrust ± oral airway as required, until return of spontaneous ventilation and consciousness.• Extubate per routine.
STANDARDIZED POSTOP ORDERS	
• Mild pain (1-3): Oxycodone 5 mg PO, may repeat x 1.• Moderate pain (4-6): Fentanyl 25 mcg IV q 5 min, for a total dose 3 mcg/kg.• Severe pain (7-10): Fentanyl 50 mcg IV q 5 min, for a total dose 3 mcg/kg.• Adjuvant analgesics: Tylenol 500 mg, may repeat x 1.• IV Demerol 12.5 mg for shivering only, may repeat x 1.• Treatment of PONV:
○ Zofran 8 mg IV x 1• If no effect, and no contraindications, add IV Promethazine 12.5 mg x 1
PACU DATA COLLECTION	
• Obtain PACU data collection sheet: Oriented x 4; Pain scores q 15 min; PAS scores q 30 min; Phase 2 ready.

STUDY PROTOCOL: THRIVE AND LARYNGOLOGIC SURGERY

THRIVE PROTOCOL	
PREOP	
• Randomize patient to THRIVE or CONTROL group. A control group is usually either a 5.0 MLT ETT or a Supraglottic HFJV.
PREINDUCTION	
• Pre-O₂ with THRIVE (FiO₂ 1.0) at 40 (30) l/min for 5 min.• Make sure the patient's head is elevated 30-40° (table in BACK UP position, not reverse Trendelenburg).
INDUCTION	
• THRIVE @ 70 l/min.• Maintain jaw thrust, with oral airway as necessary, for 3 min before surgeon starts suspension laryngoscopy. Continue jaw thrust as necessary, until patient is in full suspension.
MAINTENANCE	
• Maintain THRIVE @ 70 l/min.• If surgery prolonged (over 30 min), institute supraglottic HFJV for at least 10 min before switching back to THRIVE. Repeat as necessary.
○ HFJV settings:
▪ Frequency: 150 cpm▪ DP (driving pressure, psi) = total body weight x 0.4 (do not exceed 45 psi)▪ FiO₂ 1.0▪ Inspiratory time 40%▪ Humidity level: maximum (8)• 5.0 MLT can be placed by surgeon either instead of, or in conjunction with jet.
EMERGENCE	
• Maintain THRIVE at 70 l/min with jaw thrust ± oral airway as required, until return of spontaneous ventilation and consciousness. Mask (SGA) ventilation, as necessary.

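### Randomisation is listed before judgement-titrated midazolam; opening the allocation after premedication would cheaply close one avoidable route to bias in the recovery times

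*Protocol*

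**What the plan says.** The Preop and Premedication row of the protocol's management table is one cell shared by both arms. Its second bullet, directly after consent, reads "Randomize the patient to either THRIVE or CONTROL group", and adds "Note: patient is blinded to the modality used". Baseline measures, folder contents and the IV follow. The seventh and last bullet is midazolam: "Midazolam 0.007 mg/kg incremental doses to achieve sufficient anxiolysis, not to exceed 0.025 mg/kg total dose, unless severe anxiety". For ages 70-80 it adds "limit total dose of Midazolam to 0.5 mg".

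The separate THRIVE Protocol table also puts randomisation in its Preop row ("Randomize patient to THRIVE or CONTROL group"). Neither document describes concealment, says when the allocation is opened, or says who gives midazolam. The first steps that differ by arm, table position and the method of pre-oxygenation, are in the next row, Pre-induction.

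On recording, end-point 3.B.x covers total anesthetic doses given intraoperatively. The folder is described as follows: "Study folder contains: consent, preop QoR15, VHI, intraop and PACU data collection sheets". No preoperative drug sheet is named.

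**The concern.** Objective 2 includes "DETERMINING POSSIBLE BENEFICIAL EFFECT OF THRIVE ON IMMEDIATE POSTOPERATIVE RECOVERY in PACU". Anesthesia duration (3.B.ii) and extubation time (3.B.v) both end at eye opening. Time to orientation and time to phase 2 readiness (3.B.xii) run from PACU arrival. All four can depend on residual sedation.

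If knowledge of the arm influences premedication, part of a difference in these times would reflect sedation and not the airway technique. There is a plausible reason for such influence. THRIVE patients receive high nasal flow while awake, at 40 (30) l/min for 5 minutes, and are then managed apneic without a tube. A clinician who knows this might give more midazolam for tolerance, or less out of caution. The direction is therefore unknown.

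A difference could also go unnoticed, because neither document commits to reporting preoperative midazolam by arm.

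**Working it through.** The plan states no figure to reproduce. The order of steps is checked by reading, and the room for discretion by arithmetic.

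**Order.** In the shared row, randomisation is bullet 2 of 7 and midazolam is bullet 7. No listed step before the Pre-induction row needs the arm, so the allocation could be opened after midazolam without disturbing any listed step.

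**Inputs from the protocol.** Increment 0.007 mg/kg; cap 0.025 mg/kg, waived for severe anxiety; 0.5 mg limit at 70-80 years. Body weights and the share of patients affected are assumptions.

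**Increments under the cap.** 0.025 / 0.007 = 3.57, so at most 3 whole increments fit: 3 × 0.007 = 0.021 mg/kg, whereas 4 × 0.007 = 0.028 exceeds 0.025. Nothing in the row requires a first dose, so the range is 0 to 0.021 mg/kg:

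- 50 kg: 0 to 1.05 mg (cap 1.25 mg)
- 70 kg: 0 to 1.47 mg (cap 1.75 mg)
- 100 kg: 0 to 2.10 mg (cap 2.50 mg)

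**Sensitivity to that reading, at 70 kg.** If at least one increment is always given, the largest difference between two patients is (0.021 − 0.007) × 70 = 0.98 mg. If part-increments are allowed up to the cap, it is 1.75 mg. Under the severe-anxiety waiver there is no stated upper limit.

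**Difference in mean dose between arms.** One increment at 70 kg is 0.007 × 70 = 0.49 mg. If knowledge of the arm moved a share f of one arm by one increment, the mean would shift by f × 0.49 mg:

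- f = 10%: 0.05 mg
- f = 50%: 0.25 mg
- f = 100%: 0.49 mg

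**Ages 70-80.** 0.5 / 0.007 = 71.4 kg and 0.5 / 0.014 = 35.7 kg. Between these weights the limit leaves 0 or 1 whole increment; above 71.4 kg it leaves only part of one. The point therefore concerns mainly patients under 70.

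**What cannot be computed.** Neither document links midazolam dose to wake-up or PACU times, so the shift in minutes is unknown.

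**The case against.** The strongest reply is that the order is inferred from a checklist. Two of the seven bullets are folder inventories, and only the next row is labelled as consecutive steps. Staff knowledge of the arm is possible but not documented. This is correct, and it is why the point is conditional. It does not settle the matter, because nothing in the plan prevents the listed order from being followed.

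Second, the dosing rule is the same in both arms, weight-based, stepped and capped, and its target is the anxiety of a patient who is blinded. That narrows the discretion but does not remove it: the number of increments and the use of the waiver remain judgements.

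Third, larger unblinded choices remain. Maintenance propofol may range from 80 to 150 mcg/kg/min. Over 30 minutes that span is 70 × 30 = 2,100 mcg/kg, or 2.1 mg/kg, which is more than the 2 mg/kg induction dose. Remifentanil and fentanyl are also titrated, and all of these are given closer to emergence. Titration to Sedline 25-50 may offset part of any midazolam difference. This stands, and it limits the importance of the point. Those channels are hard to close, however, since staff cannot be blinded from pre-induction onward; this one is avoidable.

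Fourth, midazolam may already be recorded, since the fields of the data sheets are not shown. That also stands. Finally, the SAP calls the results exploratory, which lowers the stakes but does not make an avoidable imbalance useful.

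**Conclusion.** The concern holds as a minor design point. As listed, the order allows the arm to be known when a discretionary sedative is chosen, and several recovery end-points can depend on that sedative. Within the cap the room for discretion is 0 to 0.021 mg/kg in whole increments, or 0 to 1.47 mg at an assumed 70 kg. The illustrative shifts in mean dose are 0.05 to 0.49 mg. The effect on recovery times is probably small, of unknown direction, and cannot be sized from the documents.

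The conclusion assumes that the row is followed in its listed order and that the person giving midazolam learns the arm at randomisation. It does not show that either happened or that any result is biased. Confidence is medium.

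**What to change.** After consent and the baseline measures, complete midazolam before the allocation is opened to the person giving it. Extend end-point 3.B.x to cover preoperative as well as intraoperative drugs, and report total midazolam (mg/kg) by arm beside the emergence and PACU times. The dosing rule need not change. Adjusting the analysis for midazolam dose is not proposed, because under the present order the dose is a post-randomisation variable.

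The cost is small. The allocation is opened a few minutes later, and reporting needs at most one added field. The Operating Room Preparation list names the 5.0 MLT and the jet ventilator ("Monsoon JV with connection tubing for suspension laryngoscope, and full humidification set up") but no high-flow device, unless the routine airway supplies in item 1 include it. That device must either be ready for every patient or be set up after allocation, which may mean a short wait after sedation. If someone has to prepare the room earlier, only the person giving midazolam must remain unaware of the arm.

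The change works only if the allocation cannot be seen or predicted beforehand. It closes this channel alone; later unblinded titration and assessor blinding are separate matters. The SAP is written in the past tense, so for data already collected only the reporting applies, provided midazolam was recorded.

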7. Patients with the history or symptoms of increased intracranial pressure or reduced intracranial compliance (e.g. headaches, nausea and vomiting, visual changes, mental changes).
8. Patients with skull base defects.
9. Patients with pulmonary hypertension who have pulmonary artery pressures above the normal range.
10. Patients with significant chronic obstructive or restrictive lung diseases, as manifested by known history of baseline chronic hypoxia and/or hypercapnia, and/or baseline room air SpO₂ < 95%.
11. Obese patients with BMI above 35 kg/m².
12. Patients with severe and poorly controlled gastroesophageal reflux disease despite medical treatment.
13. Patients with hiatal hernia and full stomach patients.
14. Patients on immunosuppressive medications.
15. Patient's refusal to participate in the study.
16. Patients who do not understand English or mentally handicapped.
17. Pregnant or breastfeeding patients.

STUDY PROTOCOL: THRIVE AND LARYNGOLOGIC SURGERY

PROTOCOL AT A GLANCE AND STUDY END-POINTS

1. Patients will be randomly assigned to either THRIVE or ETT (control group). Patient with supraglottic jet ventilation will also be included in ETT group, if JV requested by surgeon.
2. Anesthetic management is standardized for both groups.
3. Study end-points:
 - A. THRIVE GROUP
 - i. Total apnea time
 - B. BOTH GROUPS
 - i. Demographic, ASA class and airway exam data
 - ii. Anesthesia duration: from induction to awake (opening eyes to command)
 - iii. Surgical duration: from picking up suspension laryngoscope to laryngoscope withdrawal
 - iv. Apnea time: from induction to spontaneous ventilation
 - v. Extubation time: from surgery stop to opening eyes to commands
 - vi. Time to suspension: from picking up suspension laryngoscope to full suspension
 - vii. Number of required repositions/adjustments of suspension laryngoscope during surgery
 - viii. Lowest SpO₂
 - ix. Hemodynamic & Sedline profile
 - x. Total doses of anesthetic drugs used intraop, including vasopressors, etc.
 - xi. Intraop complications
 - xii. PACU recovery profile:
 - Time to AO x 4: from arrival to PACU
 - Time to PACU phase 2-ready: from arrival to PACU
 - Pain and PAS scores
 - IV and PO opioid requirements
 - PO non-opioid requirements (PO Tylenol)

STUDY PROTOCOL: THRIVE AND LARYNGOLOGIC SURGERY

- Shivering: incidence; IV Demerol requirements
- PONV profile (nausea and vomiting incidence); IV Zofran/Phenergan requirements

xiii. Immediate postop complications

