PRE-INDUCTION: CONSECUTIVE STEPS	
Start with OR table 180°.
 
Place standard ASA monitors, Sedline, and peripheral nerve stimulator (TOF ulnar nerve)
 
 • Pre-O₂ with THRIVE (FiO₂ 1.0) at 40 (30) l/min for 5 min. • Maintain patient's head is elevated 30-40° (table in BACK UP position, not reverse Trendelenburg). 	
OR table in standard position.
 
Preoxygenate for 5 min or until FeO₂ > 0.9.

	
 • IV fluid loading completed: 5 ml/kg. • IV Glycopyrrolate 0.2 mg if HR ≤ 50 bpm for elderly patients (70-80 y.o.). • Assure all surgical supplies are ready for immediate use in THRIVE group. • Both anesthesia and surgical time-outs completed. 	

STUDY PROTOCOL: THRIVE AND LARYNGOLOGIC SURGERY

INDUCTION	
 • IV Remifentanil 1 mcg/kg, Propofol 2mg/kg IV, Rocuronium 0.6 mg/kg IV, no IV lidocaine. • Additional Remifentanil 0.5 mcg/kg and/or Propofol 0.5 mg/kg IV boluses, as required during video or suspension laryngoscopy, per hemodynamic responses and Sedline readings. 	
	
 • Turn THRIVE to 70 l/min; mask ventilation if required. • Maintain jaw thrust, with oral airway as necessary, for 3 min, before surgeon starts suspension laryngoscopy. Continue, as necessary until patient is in full suspension. • Suspension laryngoscopy by surgeon in 3 min. 	
 • Mask ventilation. • Intubate when TOF is 0, with 5.0 MLT tube and video laryngoscopy (Glidescope or Storz CMAC), secure ETT to chin in left corner of the mouth. • If Jet is used, suspend when TOF is 0.
MAINTENANCE	
 • TIVA + THRIVE (FiO₂ 1.0) at 70 l/min. • NBP q 5 min, unless indicated more frequently. • If SpO₂ < 90%, or ventricular arrhythmias, discuss with surgeon converting to the following options: 
 ○ Supraglottic or Infraglottic HFJV ○ 5.0 MLT ○ 5.0 MLT with intermittent apnea technique • If surgical duration more than 30 min, institute supraglottic HFJV per THRIVE protocol, for at least 10 min. See jet settings in THRIVE protocol. 	

STUDY PROTOCOL: THRIVE AND LARYNGOLOGIC SURGERY

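### The protocol requires surgical supplies to be ready before induction only in the THRIVE group, so part of any shorter anesthesia or surgical time could reflect preparation; the size of the effect cannot be derived

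*Protocol*

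**What the plan says.** The pre-induction part of the protocol's management table has a column for each group and then a row common to both. That common row lists fluid loading, a conditional glycopyrrolate step, a supply check and the time-outs. Only the supply check is limited to one arm: "Assure all surgical supplies are ready for immediate use in THRIVE group". The time-out item has no such limit: "Both anesthesia and surgical time-outs completed".

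The section Operating Room Preparation applies to all cases. It opens with "All drugs, airway supplies, eye tape, per routine" and goes on to the tube, video laryngoscope, jet ventilator, pumps and monitors. It names no surgical instruments. Item 2 of Protocol at a Glance and Study End-Points says "Anesthetic management is standardized for both groups", which does not extend to surgical preparation.

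Study Objectives, item 1, states the expectation: "THRIVE should improve operating conditions, decrease surgical time, and potentially lead to better patient outcomes". The time end-points are listed under 3.B for both groups.

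**The concern.** Having instruments ready before induction is possible in either arm. Where it is required in one arm only, a case-flow advantage may go to that arm for reasons unrelated to how the patient is oxygenated. Randomization does not protect against this, because the difference arises after allocation. Blinding does not help either: the preoperative part of the table states only that the patient is blinded, and an instruction that differs by arm requires staff to know the arm.

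What is at stake is the attribution of a time difference. Any bias would run in the direction the protocol expects, towards shorter times with THRIVE. The SAP could not remove it. It describes unadjusted t-tests and a chi-square test for patient characteristics, and provides nothing to separate a preparation effect from a THRIVE effect.

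**Working it through.** The documents give no sample size, standard deviation, expected effect or supply delay, so there is no figure to reproduce. The check is whether a wait for supplies falls inside each end-point's clock.

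**Clocks (Protocol at a Glance and Study End-Points, 3.B)**
- Anesthesia duration (ii) runs from induction until the patient opens the eyes to command.
- Surgical duration (iii) is defined as "Surgical duration: from picking up suspension laryngoscope to laryngoscope withdrawal".
- Time to suspension (vi) starts at the same pick-up and ends at full suspension.

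**Notation.** Let A be the mean wait for supplies between induction and pick-up. Let B be the mean wait between pick-up and withdrawal, and S the part of B that falls before full suspension. Subscripts C and T denote control and THRIVE.

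**Contribution of waiting to the control-minus-THRIVE difference**

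| End-point | Contribution |
|---|---|
| Anesthesia duration (ii) | (A_C + B_C) − (A_T + B_T) |
| Surgical duration (iii) | B_C − B_T |
| Time to suspension (vi) | S_C − S_T |

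**Per minute of extra control-arm waiting**
- One minute before pick-up adds 1 min to (ii) and 0 min to (iii) and (vi).
- One minute after pick-up adds 1 min to both (ii) and (iii). It reaches (vi) only if something needed for suspension is missing while the laryngoscope is already in hand.

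This assumes that the wait does not shorten a later step.

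**Effect of the instruction.** In the THRIVE group, supplies that are late should hold up induction, and time before induction counts in none of these end-points. The step therefore pushes A_T and B_T towards zero. For controls nothing fixes A_C or B_C. They may also be zero, but the protocol does not make them so.

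**Other differences inside the anesthesia clock.** The THRIVE column starts with the table at 180°, has no planned intubation, and schedules "Suspension laryngoscopy by surgeon in 3 min". The control column starts with the table in standard position. It then has mask ventilation until the train-of-four count is 0, followed by intubation and securing of the tube, or by suspension if jet ventilation is used. These differences also affect (ii), so supply readiness is one of several explanations for a difference there.

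**The case against.** The strongest reply is that readiness belongs to the technique. Study Objectives, item 1, names carbon dioxide build-up in the apneic patient as the main limit on how long THRIVE can be given, and suspension is scheduled soon after induction. Missing instruments would use up that time. Controls are ventilated, so they do not face the same limit. On this view the trial compares two airway strategies, each with its own set-up.

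That explains why the step is needed for THRIVE. It does not explain leaving it out for controls, where it is equally feasible. If the view is accepted, the time results describe the whole package and the protocol should say so.

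Three further replies stand:
- Silence about control supplies is not evidence that they are unready. The time-outs apply to both arms, although their content is not described, and the control airway steps leave time in which supplies could be prepared. The real wait may be close to zero.
- A reader might infer that the step acts directly on all three time end-points. The definitions do not support this: two of the three clocks start only at pick-up.
- A reader might also infer that readiness goes unrecorded. The content of the intraoperative data sheet is not in the documents. One can say only that readiness is not among the listed end-points.

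**Conclusion.** The protocol as written creates a difference in preparation between the arms that favours THRIVE and could easily be avoided. Anesthesia duration is the most exposed end-point, because it counts waits both before and after pick-up. Surgical duration is exposed only to waits after pick-up, and time to suspension hardly at all.

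The size of any bias cannot be derived. For each end-point it equals the between-arm difference in waiting that falls inside the clock, and the documents give no value for it. A reader might assume a wait of 1 to 3 min in cases of 15 to 30 min and quote a spurious advantage of 1/30 = 3.3% to 3/15 = 20% of surgical duration. That range should not be used. The wait is assumed, only the 30 min limit on procedure length is in the protocol, and the calculation needs the whole wait to fall after pick-up in controls with none in the THRIVE group.

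It would also go too far to say that a shorter time with THRIVE would be an artefact, or that the statement on standardized anesthetic management is contradicted. The first needs evidence of control-arm delay, and the second statement does not cover surgical supplies. No primary end-point is named and the SAP calls the results exploratory. The point is thus a modest one about attribution.

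**What to change.** - Reword the supply check in the common pre-induction row so that it applies to both groups before induction.
- Record its completion, and any supply-related delay with the time at which it occurred, for every patient on the existing intraoperative sheet. The time shows whether the delay fell before or after pick-up, and so which end-points it affects.
- If the sponsor regards readiness as part of THRIVE and keeps the step in that arm only, say so in the protocol and describe the time comparisons as effects of THRIVE plus its set-up, not of the oxygenation method alone.
- The SAP is dated June 2019 and written in the past tense, so enrolment may already be complete. In that case, report the difference in instructions between the arms and use the same description of the time comparisons.

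The cost is a few words in the table, a tick box and a short delay entry where one applies. The preparation itself is already required for THRIVE cases.
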